5.0 Study Procedures

Subjects will take the study medicine daily. They will return for a study visit at weeks 4, 12, 24 and at end of study at week 26. The study visits for weeks 4 and 12 should last about four hours and study visit at week 24 will last about eight hours, and the end of the study visit at week 26 will last about two hours. Total amount of time in the study is about 32 weeks, with six weeks allowed between the screening and randomization visits.

The following study procedures will take place at Week 4:

1. study staff will review medical records with the subject
2. subjects will be asked about any problems they are having
3. subjects will bring back unused medicine to monitor medication compliance
4. subjects will be asked about any medications taken, including supplements
5. subjects will receive sufficient amount of medicine to last until the next study visit approximately eight weeks later
6. AUDIT questionnaire will be administered to detail alcohol use and subjects must score less than 8 to continue participating in the study
7. female subjects of childbearing potential will undergo a urine pregnancy test and the test must be negative to continue participating in the study
8. vital signs will be taken, including height and weight
9. waist and hip circumference will be measured
10. subjects will undergo a focused physical examination
11. transient elastography (FibroScan®) will be performed by a trained technician to measure steatosis by Controlled Attenuation Parameter (CAP) and fibrosis by liver stiffness (LSM)
12. historical laboratory values will be captured from the medical records, including
 - a. HIV viral load
 - b. CD4 count

The following study procedures will take place at Week 12:

1. study staff will review medical records with the subject
2. subjects will be asked about any problems they are having
3. subjects will bring back unused medicine to monitor medication compliance

Vitamin E for NASH Treatment in HIV Infected Individuals

4. subjects will be asked about any medications taken, including supplements.
5. subjects will receive sufficient amount of medicine to last until the next study visit approximately twelve weeks later.
6. AUDIT questionnaire will be administered and subjects must score less than 8 to continue participating in the study
7. female subjects of childbearing potential will undergo a urine pregnancy test and the test must be negative to continue participating in the study
8. vital signs will be taken, including height and weight
9. waist and hip circumference will be measured
10. subjects will undergo a focused physical examination
11. transient elastography (FibroScan®) will be performed by a trained technician to measure steatosis by Controlled Attenuation Parameter (CAP) and fibrosis by liver stiffness (LSM)
12. historical laboratory values will be captured from the medical records, including
 - a. HIV viral load
 - b. CD4 count
13. approximately 50 mL of blood will be drawn to measure serum alpha- and gamma-tocopherols with the remaining amount used for future research.

The following study procedures will take place at week 24 (end of study visit):

1. study staff will review medical records with the subject
2. subjects will be asked about any problems they are having
3. subjects will bring back unused medicine to monitor medication compliance
4. subjects will be asked about any medications taken, including supplements
5. AUDIT questionnaire will be administered to detail alcohol use
6. vital signs will be taken, including height and weight
7. waist and hip circumference will be measured
8. subjects will undergo a focused physical examination
9. transient elastography (FibroScan®) will be performed by a trained technician to measure steatosis by Controlled Attenuation Parameter (CAP) and fibrosis by liver stiffness (LS).
10. approximately 50mL of blood during a fasting state will be collected for the following tests:
 - a. liver profile
 - b. complete blood count
 - c. lipid
 - d. insulin
 - e. glucose
 - f. INR
 - g. MDA
 - h. K-18
 - i. TNF-alpha
 - j. IL-10
 - k. alpha and gamma-tocopherols
11. An MRI will be performed to measure hepatic fat content by PDFF according to the established protocol.

Approximately two weeks after the Week 24 end of study visit, subjects will return for a follow-up visit. The following procedures will take place at this visit:

1. The study staff will review medical records with the subject.

Vitamin E for NASH Treatment in HIV Infected Individuals

2. Subjects will be asked about any problems they are having.
3. Subjects will be asked about any medications taken, including supplements.
4. Subjects will undergo a focused physical examination.

Upon completion of this visit, subjects will have completed their participation in the study.

	Screening	Treatment Phase (weeks)				Follow-up
		Randomize	4	12	24	
Consent & reaffirmation	X	X				
Baseline medical history	X					
Interval medical history and anthropometric measurements		X	X	X	X	
AUDIT questionnaire	X	X	X	X	X	
Assessment of compliance			X	X	X	
Review of concomitant medicines	X	X	X	X	X	
Review of adverse events			X	X	X	X
Physical examination	X	X	X	X	X	X
Dispensing study medicines		X	X	X		
Blood sample collection		X		X	X	
Urine pregnancy test	X	X	X	X	X	
Liver stiffness and CAP by TE		X	X	X	X	
MR-PDFF		X				X
Biobanking		X	X	X	X	

6.0 Reporting of Adverse Events or Unanticipated Problems involving Risks to Participants or Others

Data will be captured systematically with regards to new medications, over-the-counter medications and supplements, alcohol intake (if any), dietary intake, and changes in weight or physical activity. Patients will be instructed not to take any new medication unless reviewed with and approved by the study PI (wherever possible). During the trial, subjects will be instructed to avoid medications or supplements that may affect the primary outcome (as detailed in the inclusion and exclusion criteria).

Vitamin E for NASH Treatment in HIV Infected Individuals

Risks of blood draw include pain and bruising at the site. Blood will be drawn by experienced personnel.

Risks of completing the questionnaires include embarrassment or being uncomfortable with the questions asked. Subjects can refuse to answer any questions to which they do not wish to respond.

Risks of transient elastography include being uncomfortable lying supine pain, soreness at the site and a small chance of allergic reaction to the ultrasound gel. These study procedures will be performed by experienced personnel.

Risks of MRI include being uncomfortable lying still for a period of time and experiencing claustrophobia (feeling closed in or trapped).

Risks of taking Vitamin E include allergic skin reactions (inflammation or itching), blurred vision, changes in cholesterol levels, changes in insulin resistance, diarrhea, dizziness, fatigue, flu-like symptoms, headache, heart conditions, increased risk of death, increased risk of fainting or falls, increased risk of heart failure, increased risk of high blood pressure in pregnancy, increased risk of stroke, increased risk of tuberculosis, kidney dysfunction, nausea, severe response to infection (in preterm babies), sexual dysfunction, stomach pain, vision loss, and weakness.

There is a risk of loss of confidentiality.

A Data Safety and Monitoring Board (DSMB) will be organized and instituted to review study and safety data as well as reporting adverse events/unanticipated problems and will meet as necessary for a thorough review of this study. The DSMB will consist of a hepatologist, an infectious disease specialist, and a biostatistician.

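### The schedule table puts the second MR-PDFF scan, the primary endpoint, at follow-up (about week 26), while the visit list and endpoint definition put it at week 24; *end of study* names both visits.

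*Protocol*

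**What the plan says.** Protocol 5.0 sets out the visits in three ways.

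- **Opening text.** "They will return for a study visit at weeks 4, 12, 24 and at end of study at week 26". It then gives visit lengths: about eight hours for week 24, while "the end of the study visit at week 26 will last about two hours". It also says "Total amount of time in the study is about 32 weeks", six of which are allowed between screening and randomization.
- **Procedure lists.** One list begins "The following study procedures will take place at week 24 (end of study visit" and has as item 11: "An MRI will be performed to measure hepatic fat content by PDFF according to the established protocol". The follow-up visit, about two weeks later, has four items: record review, problems, medications and a focused physical examination. It has no MRI.
- **Schedule table.** As extracted, the MR-PDFF row is marked at Randomize and Follow-up, and its week-24 cell is empty. The row "Liver stiffness and CAP by TE" is marked from Randomize through week 24. The row "Dispensing study medicines" has its last mark at week 12.

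Protocol 2.0 gives both groups 24 weeks of treatment and places the second scan at the end of treatment. Protocol 8.0 and the SAP use the same text: all endpoints are 24-week changes from baseline, the primary outcome is the change at the end of treatment, and the MR-PDFF scans are timed at baseline and *end of study*.

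**The concern.** MR-PDFF is scheduled only once after baseline, so its row in the table times the whole primary outcome. A coordinator working from the table would book the scan for the follow-up visit. That is about two weeks after the 24-week treatment period and about two weeks after the blood and elastography measurements that supply the secondary endpoints.

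The definition in Protocol 8.0 and the SAP does not fully protect against this, because it times the scan by *end of study*, and Protocol 5.0 attaches that label to week 26 in one place and to week 24 in another. Someone who combines the opening text of 5.0 with the table arrives at week 26. Someone who uses the procedure lists arrives at week 24.

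The trial runs at two sites with about 28 participants each. If they read the schedule differently, the primary measurement would mix scans taken at the end of treatment with scans taken after it.

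**Working it through.** **1. Reproduce the stated duration.** Inputs from Protocol 5.0: up to 6 weeks from screening to randomization, 24 weeks to the week-24 visit, and about 2 weeks more to follow-up.

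6 + 24 + 2 = 32 weeks, which matches the stated total. The Follow-up column is therefore the week-26 visit.

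**2. Read the table.** Both header lines and all 14 rows split into the same seven cells: label, Screening, Randomize, 4, 12, 24, Follow-up.

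- Week 24 is marked in 10 of 14 rows. The four without a mark are consent, baseline history, dispensing and MR-PDFF.
- Follow-up is marked in 3 rows: adverse events, physical examination and MR-PDFF. The first two match items 2 and 4 of the follow-up list. MR-PDFF matches none of its four items.
- Of the three rows that carry endpoint measurements, blood and elastography are marked at week 24, as in the week-24 list. Only MR-PDFF is not.

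**3. Set the sources side by side.**

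| Source | Second MR-PDFF scan |
|---|---|
| Protocol 2.0 | end of treatment (24 weeks) |
| Protocol 5.0, week-24 list, item 11 | week 24 |
| Protocol 5.0, follow-up list | no MRI |
| Protocol 5.0, schedule table (as extracted) | Follow-up, about week 26 |
| Protocol 8.0 and SAP, endpoint window | 24 weeks |
| Protocol 8.0 and SAP, primary outcome | end of treatment |
| Protocol 8.0 and SAP, scan timing | *end of study*: week 26 in the opening of 5.0, week 24 in the list heading |

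**4. Is the follow-up visit off drug?** At week 12, "subjects will receive sufficient amount of medicine to last until the next study visit approximately twelve weeks later". Week 12 + about 12 weeks = week 24. The table shows no later dispensing, and unused medicine is brought back at week 24. On the documents' own supply schedule, a scan at follow-up is about two weeks after the last dose.

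**5. Size of the discrepancy.** 26 × 7 = 182 days; 24 × 7 = 168 days; 182 − 168 = 14 days; 2/24 = 8.3% of the stated interval.

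No sample-size or power figure depends on this point.

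**The case against.** The strongest reply is that the main evidence is one cell of a table read from a PDF. A uniform seven-cell grid does not prove that each mark landed in the right column: a mark shifted by one column still leaves seven cells. MR-PDFF is also the only row with a run of several blanks between two marks, so correctly placed neighbours give limited reassurance. This stands in part. A shift confined to one row cannot be excluded, and the cell must be checked against the original. The conflict over *end of study*, however, is in running text and does not depend on the table.

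Second, the rest of the text settles on week 24: the MRI is item 11 of that list, the visit lengths favour the eight-hour visit, and in Protocol 8.0 and the SAP the 24-week window is stated immediately before the scan is timed. This is right about intent, and it is why the cell is most likely a drafting error. It does not make the table correct.

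Third, the table departs from the lists elsewhere. It has no follow-up mark for concomitant medicines although follow-up item 3 asks about them, it marks a week-24 pregnancy test that the week-24 list omits, and it marks a screening physical examination that the screening list in Protocol 4.0 does not name. Nothing gives the table precedence over the lists. That is true, and moving one mark will not reconcile the whole table. Those rows, however, do not carry the primary endpoint.

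Fourth, no consequence is shown. That stands and limits the conclusion below.

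**Conclusion.** The concern holds: as written, the protocol gives two times for its only post-baseline primary measurement, and the label used in the endpoint definition points to both. The discrepancy is about two weeks and puts the table's scan off treatment.

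The effect on the trial's result cannot be quantified from these documents and may be nil. Nothing shows that either site scanned at follow-up. Scan timing is not tied to treatment arm, so no between-arm bias is claimed, nor any loss of power.

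The table part assumes that the extracted cell matches the original; the label part needs no such assumption. The need to correct this rests on what the error touches, not on a demonstrated effect.

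**What to change.** 1. Check the MR-PDFF row against the original protocol. If it reads as extracted, move the second mark from Follow-up to week 24.
2. In Protocol 5.0, give *end of study* one meaning in both the opening text and the procedure lists.
3. In Protocol 8.0 and the SAP, time the MR-PDFF scans at baseline and week 24 (end of treatment).
4. If any second scans were taken at the follow-up visit, report their dates and add a sensitivity analysis of the primary outcome for scan timing.

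The cost is one table cell, one consistent label and one phrase in each document. No scan is added, and the sensitivity analysis is needed only if follow-up scans exist. The other table mismatches noted above can be reconciled in the same edit.

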3.0 Inclusion/Exclusion Criteria

Inclusion criteria:

1. males and females ≥21 years with biopsy-proven NASH within 6 months prior to enrollment
2. histological diagnosis of NASH will be confirmed by an experienced liver pathologist before study entry
3. HIV infection
4. stable dose of anti-diabetic agents and ART in the 3 months preceding enrollment and expected by the physician treating diabetes and HIV to remain on stable medications during the study
5. stable dose of tesamorelin in the 6 months preceding enrollment
6. willingness to participate in the study
7. ability to understand and give informed consent for participation
8. willing to stop use of Vitamin E and/or multivitamins containing Vitamin E at time of enrollment and for the duration of participation in the study

Exclusion Criteria:

1. Presence of other chronic liver diseases (hepatitis B or C, autoimmune hepatitis, cholestatic liver disease, Wilson disease, hemochromatosis, etc.)
2. average alcohol consumption >3 drinks/day for men or >2 drinks/day for women in the 6 months prior to enrollment.

Vitamin E for NASH Treatment in HIV Infected Individuals

3. Alcohol Use Disorder Identification Test (AUDIT) score 8 or more
4. ongoing use of medications known to cause hepatic steatosis (e.g., corticosteroids, amiodarone, methotrexate, tetracycline, tamoxifen, estrogens at doses greater than those used for birth control, anabolic steroids, or valproic acid)
5. prior bariatric surgery
6. severe co-morbidities (e.g., advanced cardiac, renal, pulmonary, or psychiatric illness, as defined as at least one suicide attempt in the past 12 months)
7. allergy to vitamin E
8. use of drugs with potential effect on NASH such as ursodeoxycholic acid, S-adenosylmethionine (SAM-e), betaine, pentoxifylline, or milk thistle in the three months prior to enrollment.
9. changing doses of statins (simvastatin, pravastatin, atorvastatin, fluvastatin, lovastatin, rosuvastatin) or fibrates (clofibrate, fenofibrate) in the three months prior enrollment.
10. illicit substance abuse within the past twelve months, except for marijuana
11. breast feeding, pregnancy, inability or unwillingness to practice contraception for the duration of the study
12. contraindications for the MRI procedure (e.g., prostheses, severe claustrophobia).
13. poorly controlled diabetes with A1C >9 within in the last six months
14. use of total parenteral nutrition in the 6 months preceding liver biopsy or enrollment

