4.0 Enrollment/Randomization

Participants found to have NASH will be reviewed for their eligibility to participate in this protocol. Eligible subjects will be contacted about this study and interested individuals will enter the screening phase of the protocol.

Screening period: Eligible subjects will be screened within six weeks prior to randomization. The following procedures will take place at the screening visit:

1. Complete explanation of the study, including all study visits and procedures and administration of the informed consent statement and HIPAA Authorization form.
2. An AUDIT questionnaire to determine alcohol consumption will be administered. Eligible subjects will be required to obtain a score of less than 8 on the questionnaire.
3. Current social and medical history will be thoroughly reviewed.
4. Inclusion and exclusion criteria will be verified during this visit.
5. Female subjects of child-bearing potential will have a urine pregnancy test and the pregnancy test must be negative to participate in the study
6. Information to be collected includes:
 - a. age
 - b. sex
 - c. race
 - d. ethnicity
 - e. past medical and medicinal history
 - f. BMI

Vitamin E for NASH Treatment in HIV Infected Individuals

- g. waist and hip circumference measurements
- h. vital signs, including blood pressure, respiratory rate, heart rate, temperature
- i. historical laboratory values from medical records, including:
 - i. serum electrolytes
 - ii. liver profile
 - iii. renal parameters
 - iv. insulin
 - v. glucose
 - vi. A1C level
 - vii. lipid profile
 - viii. HIV viral load
 - ix. CD4 count

Randomization-baseline evaluation visit

1. Subjects will return no more than six weeks after the completion of the screening visit for a baseline evaluation and randomization into the study. All eligible subjects who have provided informed consent and who have met all the inclusion criteria and none of the exclusion criteria will have multiple evaluations performed prior to randomization. This baseline evaluation will be conducted in a single study visit. Subjects will be asked to fast overnight and will undergo the following activities: review of medical history
2. detailed review of medications history
3. administration of the AUDIT questionnaire to capture alcohol use with a score less than 8 in order to participate in the study
4. collection of vital signs
 - a. height
 - b. weight
 - c. blood pressure
 - d. heart rate
 - e. respiratory rate
 - f. temperature

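### The AUDIT limit at weeks 4 and 12 ends study participation before the only outcome scan, so anyone removed gives no data to the primary ANCOVA; the likely effect is small and the remedy cheap

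*Protocol*

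**What the plan says.** Protocol section 5.0 sets a continuation condition at two visits after randomisation. Week 4 item 6: "AUDIT questionnaire will be administered to detail alcohol use and subjects must score less than 8 to continue participating in the study". Week 12 item 6: "AUDIT questionnaire will be administered and subjects must score less than 8 to continue participating in the study".

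The same threshold is applied before randomisation. It is an exclusion criterion in section 3.0 ("Alcohol Use Disorder Identification Test (AUDIT) score 8 or more"). Section 4.0 checks it at screening ("Eligible subjects will be required to obtain a score of less than 8 on the questionnaire") and again at the baseline visit ("administration of the AUDIT questionnaire to capture alcohol use with a score less than 8 in order to participate in the study").

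The outcome scan appears in the week 24 list, item 11: "An MRI will be performed to measure hepatic fat content by PDFF according to the established protocol". The schedule table, as extracted, marks the second MR-PDFF under Follow-up instead. Either way it falls after weeks 4 and 12, and no other post-baseline scan is planned.

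Protocol section 8.0 and the SAP define the primary outcome as the change in MR-PDFF from baseline to the end of the study. It is analysed by ANCOVA on treatment, baseline demographics and baseline liver fat. Section 7.0, despite its title, gives no withdrawal visit, exit scan or follow-up after removal. Neither document defines an analysis set or a method for missing outcomes.

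**The concern.** The protocol itself can cause primary outcomes to be lost, through a variable measured after randomisation. It treats that variable as relevant to the disease: besides the AUDIT criterion, section 3.0 excludes "average alcohol consumption >3 drinks/day for men or >2 drinks/day for women in the 6 months prior to enrollment". Ordinary drop-out cannot be fully prevented, but this loss follows from a written instruction and can be avoided.

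Recruiting 28 to obtain 25 per group replaces lost numbers. It does not undo selection, and neither does adjustment for baseline covariates when selection depends on a later score. Section 8.0 gives the pilot's main purpose as estimating the average improvement in liver fat and its spread, for use in later trials. Under the rule, those estimates describe participants who stayed below 8 at weeks 4 and 12, not everyone randomised. An outcome that was never measured cannot be recovered at the analysis stage.

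**Working it through.** **Sequence in the text.** AUDIT below 8 at screening and at baseline; randomisation; AUDIT below 8 required to continue at weeks 4 and 12; outcome scan at week 24 (or Follow-up, per the table). A participant removed at week 4 or 12 has a baseline scan only, so no change score exists.

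**The plan's own figures.** Inputs from section 8.0 and the SAP: 25 per group, alpha 5% (taken as two-sided), two-sample t-test with equal variances. Noncentral t power is 91.9% at effect size 0.97 (stated 91%) and 80.1% at 0.81 (stated 80%). Drop-out: 25/0.9 = 27.8, so 28 per group; 28 × 0.9 = 25.2. These reproduce.

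**Assumed inputs.** The documents give neither a removal rate nor the effect of alcohol on fat change. Let k of 28 be removed per arm (k = 0 to 3), so p = k/28. Let those removed have a fat change m SD worse than those retained (m = 0.5 to 1.5).

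- Overstatement of an arm's mean improvement = p × m.
- Understatement of the SD = 1 − 1/√(1 + p(1 − p)m²).

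| k per arm | m (SD) | Mean overstated (SD) | SD understated |
|---|---|---|---|
| 0 | any | 0 | 0% |
| 1 | 0.5 | 1/28 × 0.5 = 0.018 | 0.4% |
| 2 | 1.0 | 2/28 × 1.0 = 0.071 | 3.2% |
| 3 | 1.5 | 3/28 × 1.5 = 0.161 | 9.3% |

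**Sampling error at 25 per arm, without covariate adjustment.**

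- Standard error of an arm mean: 1/√25 = 0.20 SD. The largest shift is 0.161/0.20 = 0.80 of this; the middle case is 0.071/0.20 = 0.36.
- Relative standard error of an estimated SD: 1/√48 = 14.4% per arm, 1/√96 = 10.2% pooled.
- Standard error of the contrast: √(2/25) = 0.283 SD.

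**Contrast between arms.** With equal removal and the same treatment effect in those removed, both arm means shift equally and the contrast is unbiased. In the extreme case of 3 removed in one arm and none in the other, at 1.5 SD, it shifts by 0.161 SD, or 0.161/0.283 = 0.57 of its standard error.

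**Power.** Unchanged while all losses together stay within 3 per group. Beyond that, power at effect size 0.81 falls by about 2 points for each further loss per group (78.4% at 24 per group).

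**The case against.** The strongest reply is that the rule is deliberate. This is a trial in nonalcoholic disease, the threshold is checked at entry and repeated at two visits, and keeping alcohol out of a liver-fat comparison is a legitimate aim. Participants have passed the threshold twice before randomisation and treatment is double-blind, so removals should be few and there is no evident reason for them to differ by arm. The magnitude rests entirely on assumed inputs, and its upper case uses the whole drop-out margin. Section 5.0 applies the same continuation wording to the pregnancy tests, and the wider gap is the absence of any withdrawal procedure or missing-data method.

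Most of this stands, and it limits the point to a minor one. It does not remove it: the aim of controlling for alcohol can be met by a sensitivity analysis without discarding outcomes.

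Two further objections also stand. First, exclusion from the ANCOVA is a consequence of the text, not a stated rule, and an unwritten practice of scanning removed participants cannot be ruled out. Second, a reader might see a contradiction in the week 24 item, which reads only "AUDIT questionnaire will be administered to detail alcohol use" and sets no limit. The documents do not support that: week 24 is labelled the end-of-study visit and includes the scan, so a condition for continuing would have little function there. No change to that item is needed.

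**Conclusion.** The point holds as a minor, cheaply remedied weakness. That the rule ends participation before the only outcome scan is plain in the text. How many participants it affects is unknown, possibly none. On the assumed ranges, an arm mean is overstated by 0 to 0.16 SD and the SD understated by 0 to 9.3%, all below one unadjusted standard error. Adjustment for baseline could make the standard errors smaller; the documents do not allow that to be quantified.

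A reader might infer that the treatment comparison is biased or the trial underpowered. Neither follows. Bias in the contrast needs removal, or the treatment effect among those removed, to differ between arms, and nothing in the documents indicates either. Power falls below the stated values only if AUDIT removals and ordinary drop-out together exceed 3 per group.

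**What to change.** **Protocol, section 5.0, week 4 item 6 and week 12 item 6.** Separate study-drug handling, which is for the sponsor to decide, from outcome follow-up. State that randomised participants who score 8 or more are asked to attend the planned week-24 assessments, including MR-PDFF. The pregnancy items are outside this change and stay with the sponsor.

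**SAP.** State that the primary ANCOVA includes every randomised participant with an end-of-study MR-PDFF, in the assigned arm, whatever the post-baseline AUDIT score. Add a sensitivity analysis restricted to participants with AUDIT below 8 throughout. Report AUDIT-related events and missing scans by arm.

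**Cost.** Wording in two protocol items and the SAP. On the assumed range, up to 6 scans (3 in each of two arms) that are already planned would be kept if those asked attend. The downsides are that a few participants with higher alcohol use remain in the primary analysis, where the sensitivity analysis shows their influence, and that some who are asked may not come. If these participants are already scanned in practice, writing it down costs almost nothing.

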5. focused physical examination
6. measurement of waist and hip circumference
7. approximately 50mL of blood during a fasting state will be collected for the following tests:
 - a. liver profile
 - b. complete blood count
 - c. lipid
 - d. insulin
 - e. glucose
 - f. INR
 - g. MDA
 - h. K-18
 - i. TNF-alpha
 - j. IL-10
 - k. alpha and gamma-tocopherols
8. female subjects of child-bearing potential will have pregnancy test and the pregnancy test must be negative to participate in the study
9. a positive urine pregnancy test will be confirmed with a serum pregnancy test

Vitamin E for NASH Treatment in HIV Infected Individuals

10. transient elastography (FibroScan®) will be performed by a trained technician to measure steatosis by Controlled Attenuation Parameter (CAP) and fibrosis by liver stiffness (LSM)
11. MRI will be performed to measure hepatic fat content by PDFF according to the established protocol

Randomization

At the same visit, after the baseline evaluation is completed, subjects will be randomly assigned to either Group A: vitamin E in the form of all natural RRR-alpha tocopherol at 800 IU/d for 6 months (n = 28) or Group B: matching placebo for 6 months (n = 28). We will use a stratified randomization plan based on one factor, diabetes, similar to the recent FLINT trial (142). This will ensure two treatment groups having similar distribution of diabetes. A stratum specific computer-generated randomization list will be prepared by the study statistician to randomly assign study subjects in one of the two treatment groups. A block size of four will be used to ensure balance in number of subjects recruited in the two groups. Participants will be given sufficient drug for daily dosing and will be given detailed instructions about how to take the medicine.

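### Kidney dysfunction is a listed risk of vitamin E, but no renal test is scheduled at baseline or on treatment, so a symptom-free renal change would not be systematically found

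*Protocol*

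**What the plan says.** Among the risks of taking vitamin E, Protocol section 6.0 names "increased risk of tuberculosis, kidney dysfunction, nausea". The same list includes changes in cholesterol and in insulin resistance.

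The laboratory content is set out visit by visit:

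- **Screening (section 4.0).** Staff collect "historical laboratory values from medical records, including" a list in which serum electrolytes, liver profile and "renal parameters" are separate entries. No date window is given.
- **Baseline (section 4.0, item 7) and week 24 (section 5.0, item 10).** At each, "approximately 50mL of blood during a fasting state will be collected for the following tests": liver profile, blood count, lipids, insulin, glucose, INR, MDA, K-18, TNF-alpha, IL-10 and tocopherols.
- **Week 12 (section 5.0, item 13).** "approximately 50 mL of blood will be drawn to measure serum alpha- and gamma-tocopherols with the remaining amount used for future research".
- **Weeks 4 and 12 (section 5.0, item 12).** "historical laboratory values will be captured from the medical records, including" HIV viral load and CD4 count, the only two named.

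The other routes to a renal event, at weeks 4, 12, 24 and follow-up, are that "study staff will review medical records with the subject" and "subjects will be asked about any problems they are having", with a focused examination. The schedule table marks adverse event review at the same four visits. Section 6.0 also sets up a DSMB to review safety data. Neither the protocol's section 8.0 nor the SAP contains a renal endpoint or a safety analysis.

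**The concern.** Loss of renal function can be silent until it is advanced, so laboratory tests are the usual way to find it. The plan names it as a risk of the study drug, draws about 50 mL of blood three times, and does not list a renal test for any of those draws.

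Three things are at stake. A participant with a symptom-free decline could complete 24 weeks of dosing without the protocol showing it. If an abnormal value did turn up through outside care, there would be no on-study baseline to set it against, only a historical value of unknown age. And the DSMB would see renal information only for participants whose outside clinicians happened to test them, at irregular times.

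**Working it through.** **1. Renal tests by visit.** The lists in sections 4.0 and 5.0, set beside the schedule table:

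| Visit | Scheduled blood tests | Renal items |
|---|---|---|
| Screening | none drawn; values from records | renal parameters, historical and undated |
| Baseline | 11 items | 0 of 11 |
| Week 4 | no blood sample collection marked | 0 |
| Week 12 | tocopherols; remainder for research | 0 |
| Week 24 | same 11 items as baseline | 0 of 11 |
| Week 26 follow-up | no blood sample collection marked | 0 |

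**2. Could the liver profile cover it?** No. The screening list names liver profile, serum electrolytes and renal parameters as three entries. The on-study panels keep the first and omit the other two.

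**3. Comparison with similar risks on the same list.** Changes in cholesterol can be followed from the lipid panel, and changes in insulin resistance from insulin and glucose, at baseline and week 24. Kidney dysfunction is also assessed in the laboratory and has no matching test.

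**4. What a test would add statistically.** The plan's own figures come first. Inputs from section 8.0 are 25 per group, alpha 5%, and a two-sample t-test with equal variance. Sidedness is not stated; two-sided is assumed. The noncentrality is d × √(n/2) with 48 degrees of freedom.

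- d = 0.97: 0.97 × √12.5 = 3.43, power 0.919 (stated 91%).
- d = 0.81: 0.81 × √12.5 = 2.86, power 0.801 (stated 80%).
- Recruitment: 25 / (1 − 0.10) = 27.8, rounded up to 28 per group, 56 in all, as planned.

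The plan's figures are reproduced to within about one percentage point. The same calculation applied to change in a continuous renal marker, with 25 completers per arm, gives a smallest difference detectable with 80% power of 0.81 SD.

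For a yes/no renal event the documents give no rates. Under rates assumed here purely for illustration, Fisher exact power (5% level, 25 per arm) is:

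| Placebo | Vitamin E | Power |
|---|---|---|
| 2% | 10% | 0.023 |
| 5% | 20% | 0.198 |
| 2% | 25% | 0.522 |
| 2% | 30% | 0.715 |

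A between-arm test would therefore show only very large effects.

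**5. Cost.** 56 participants × 3 existing draws = 168 assays at most; drop-out lowers this.

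**The case against.** The strongest reply is that the plan is not blind to renal harm. Record review, questioning, examination and adverse event review all occur at weeks 4, 12, 24 and follow-up. The record capture at weeks 4 and 12 is introduced by the word including, so it is not clearly closed to other results. A charted renal diagnosis could be recorded and passed to the DSMB. This stands. It rules out three stronger conclusions that a reader might draw:

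- *That the trial cannot detect kidney dysfunction in any patient or compare it between arms.* Symptomatic or charted events can be found and could be counted by arm, although no such analysis is specified.
- *That none of the 56 participants would have a renal value during the study.* The documents support only that the protocol schedules no renal test. Values from outside care may exist in the records reviewed.
- *That section 7.0 would carry a false all-clear into later trials.* That section makes larger trials conditional on benefit to liver fat and NASH markers, and leaves those trials to evaluate safety as well as efficacy. No renal-safety conclusion is planned here.

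It is also fair to say that the risk list is broad, that tuberculosis, stroke and vision loss have no scheduled test either, and that no frequency is given for kidney dysfunction. Nothing in the documents requires an assay for every listed risk. The narrower argument is that this risk can be measured in blood already being drawn, as is done for two others on the list.

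Two further mitigations are partial. Exclusion criterion 6 cites advanced renal illness, which reduces risk at entry but does not measure change. Biobanking from randomization to week 24 might allow a retrospective assay, but none is planned and it would not inform safety review in real time.

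**Conclusion.** The gap is real but limited. A plan followed exactly produces no scheduled renal value at baseline or during 24 weeks of dosing, for a risk that the protocol itself attributes to the study drug. Clinically evident events may be captured; symptom-free laboratory changes would be captured only by chance.

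The primary endpoint and its analysis are unaffected. The value of adding the test lies in individual safety and a descriptive safety record. It does not lie in hypothesis testing, since about 0.81 SD is the smallest difference detectable with 80% power at 25 per arm (two-sided 5%, equal variances).

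The conclusion rests on reading the panel lists as complete, and on the liver profile not including renal tests, which the separate entries at screening support. It does not depend on any assumed renal event rate. Because the remedy is cheap, the change is worth making.

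**What to change.** Reconcile the risk list in section 6.0 with the laboratory lists. The simplest way is to add serum creatinine, with eGFR, to the tests run on blood already drawn at baseline (section 4.0, item 7), week 12 (section 5.0, item 13) and week 24 (section 5.0, item 10). In section 8.0 and the SAP, add a sentence that change from baseline will be summarized by arm alongside adverse events, as description without a significance test.

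This adds a measurement only. Whether and how to act on a result is for the sponsor and the DSMB to decide.

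The cost is a short protocol amendment and at most 168 routine assays, with no new visit, blood draw or staff. If the sponsor prefers not to add the test, the protocol should say why this listed risk is left to record review and adverse event reporting, and trial reports should state that renal function was not systematically measured.
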